This Statistical Analysis Plan (SAP) details the statistical methodology to be used in analyzing trial data and outlines the key statistical programming specifications. It describes the variables and populations, anticipated data transformations and manipulations, and other details of the analyses not provided in the trial protocol. The SAP is written based on recommendations from *ICH E3: Structure and Content of Clinical Study Reports*, and *ICH E9: Statistical Principles for Clinical Trials*. Table, figure and listing shells are described in a separate document.

This SAP will be followed completely for the analysis of data derived from the clinical trial. Changes to the protocol planned analyses are described in Section 4.7. If any unforeseen additional analyses are included in the clinical study report (CSR) they will be clearly described as additional, unplanned analyses in Section 4.7 if added prior to database lock, or to the equivalent section of the CSR if ad-hoc analyses are requested post-database lock.

1.1 Objectives, Endpoints, and Estimands

This is a phase 2 trial of adult subjects who are seropositive or seronegative for SARS-CoV-2 at baseline. Immunogenicity, tolerability, and safety data will be included in the analysis and CSR for this trial.

Objectives	Endpoints
Primary	
To assess SARS-CoV-2 specific humoral immune responses of the ABNCoV2 vaccine in initially SARS-CoV-2 seronegative and seropositive subjects.	
Primary:
 
SARS-CoV-2 neutralizing antibody titers at 2 weeks after the last vaccination, i.e., after the second vaccination in initially seronegative subjects (Group 1) and after the single boost vaccination in initially seropositive subjects (Groups 2 and 3), for subjects in the Immunogenicity Analysis Set (Section 4.1.2).
 
Sensitivity Analyses:
 
SARS-CoV-2 neutralizing antibody titers at 2 weeks after the last vaccination for all vaccinated subjects (Safety

Objectives	Endpoints
	
Analysis Set) with at least one post-vaccination neutralizing antibody titer as an observed case analysis. Additionally, a multiple imputation analysis will be performed using the Safety Analysis Set for a full accounting of the trial population.
 
Supportive Endpoints: SARS-CoV-2 neutralizing antibody response, defined as achieving SARS-CoV-2 neutralizing antibody titers above the limit of quantification in Group 1, or having an at least a 2-fold or 4-fold increase from baseline in Groups 2 and 3, respectively, for subjects in the Immunogenicity Analysis Set.


Secondary
 
To assess the safety and tolerability of the ABNCoV2 vaccine in adult seropositive and seronegative subjects.
	
Secondary:
 
 Subjects reporting any Serious Adverse Events (SAEs) or Adverse Events of Special Interest (AESIs) assessed as related to trial vaccine within 8 days after vaccination Subjects reporting any Grade 3 or higher Adverse Events (AEs) assessed as related to trial vaccine within 8 days after vaccination For the primary analysis of these endpoints, if the investigator confirms the subject discontinues the trial within 8 days after vaccination due to AEs, the subject is considered having a related SAE/AESI/Grade 3 or higher AE regardless of the seriousness, severity, or causality of the AE for which the subject discontinued. This is consistent with the “composite” strategy. 
Sensitivity Analyses:
 
 Subjects who discontinue the trial within 8 days after vaccination due to AE will be analyzed using the “treatment policy” strategy to handle the intercurrent event, where the subject will not be considered having a related SAE/AESI/Grade 3 or higher AE assessed as related to trial vaccine, unless the specified AE leading to discontinuation meets one or more of these categories.

Objectives	Endpoints
	
Supportive Endpoints:
 
 Subjects reporting any SAE or AESI, regardless of relationship, within 29 days after vaccination. Subjects reporting any Grade 3 or higher AEs assessed as related to trial vaccine within 29 days after vaccination. Subjects reporting solicited local AEs within 8 days after vaccination. Subjects reporting solicited general AEs within 8 days after vaccination.

Exploratory
 
 To assess SARS-CoV-2 specific peak humoral immune responses after the prime-boost regimen (Group 1) or the booster dose (Group 2 and Group 3) of the ABNCoV2 vaccine. To explore SARS-CoV-2 specific cellular immune responses to the ABNCoV2 vaccine. To assess SARS-CoV-2 specific neutralizing immune responses against variant strains circulating at the time of analysis. 	
 a) SARS-CoV-2 neutralizing antibody titers at 2 and 4 weeks post-prime vaccination and 1, 4, and 13 weeks post-boost vaccination (Group 1), and 1 week, 4 weeks, 3 months, 6 months, 1 year and 2 years after vaccination (Groups 2 and 3). b) Frequency and percentage of subjects in Groups 2 and 3 with SARS-CoV-2 neutralizing antibody titers having an at least 2-fold increase and 4-fold increase, respectively, from baseline at each sampling time point. c) SARS-CoV-2 total antibody titers (by ELISA) at all sampling time points. Cellular immune response, by Interferon-γ / Interleukin-4 ELISPOT, at 1 week after the last vaccination for all subjects. SARS-CoV-2 neutralizing antibody titers against variant strains circulating at the time of analysis at 2 weeks after last vaccination for all subjects.

Primary Estimand

The primary clinical question of interest is: What peak SARS-CoV-2 neutralizing antibodies titers can be achieved in seronegative (Group 1) and seropositive (Groups 2 and 3) adult subjects after protocol-specified vaccination regimen with ABNCoV2?

Treatment Condition: open-label, non-randomized treatment where subjects follow the protocol requirements and have no deviations from the protocol which would affect their SARS-CoV-2 neutralizing antibody titer levels at two weeks post the last vaccination with ABNCoV2.

Population: Seronegative (Group 1) or seropositive (Groups 2 and 3) adult subjects who meet all of the inclusion and none of the exclusion criteria for the trial, have their 2 weeks post-last vaccination neutralizing antibody titer result, and have no protocol violations which would affect the immunogenicity assessment for the trial.

Endpoint: SARS-CoV-2 neutralizing antibody titer at 2 weeks post-last vaccination (second vaccination for Group 1, and single boost vaccination for Groups 2 and 3).

Intercurrent Events:

1. Development of COVID-19 symptoms prior to 2 weeks after the last vaccination (Week 6 in Group 1 and Week 2 in Groups 2 and 3) and having a positive test for SARS-CoV-2 infection.

Note, subjects who come in contact with the virus can have significant interference with the SARS-CoV-2 neutralizing antibody levels and thus will be excluded from the primary analysis. This is equivalent to the “while on treatment” strategy.

2. Discontinuation due to AEs from either the second vaccination (Group 1) or the trial (all groups).

Note, for the primary estimand the second intercurrent event is not considered as having an impact on the SARS-CoV-2 neutralizing antibody levels and therefore the “treatment policy” strategy will be used.

Population-level summary:

Group 1 - Geometric mean of SARS-CoV-2 neutralizing antibody titers at 2 weeks after the second vaccination.

Groups 2 and 3 - Geometric mean of the fold increases, defined as the ratio of SARS-CoV-2 neutralizing antibody titer at 2 weeks post single boost vaccination divided by the neutralizing antibody titer at baseline (last measurement prior to ABNCoV2 vaccination).

Rationale for estimand: The primary estimand will allow Bavarian Nordic (BN) in this early phase trial to understand the immunogenic effect of the ABNCoV2 vaccine in subjects treated per protocol specifications to inform future later phase trials.

Secondary Estimands

The secondary clinical questions of interest are:

- What percentage of subjects experience an SAE or AESI assessed as related to trial vaccination within 8 days after vaccination?
- What percentage of subjects experience a Grade 3 or higher AE assessed as related to trial vaccination within 8 days after vaccination?

Treatment Condition: open-label, non-randomized treatment where subjects receive at least one vaccination.

Population: Seronegative (Group 1) or seropositive (Groups 2 and 3) adult subjects who meet all of the inclusion and none of the exclusion criteria for the trial, and have received at least one trial vaccination.

Endpoints: Occurrence of a related SAE, AESI, or Grade 3 or higher AE within 8 days after vaccination.

Intercurrent Events: Discontinuation due to AEs from either the second vaccination (Group 1) or the trial (all groups). If it is confirmed by the investigator that the subject discontinues the trial within 8 days after vaccination due to AEs, the subject is considered having a related SAE/AESI/Grade 3 or higher AE regardless of the seriousness, severity, or causality of the AE for which the subject discontinued. This is consistent with the “composite” strategy.

Note, including subjects who withdraw due to AEs within 8 days after vaccination as having had an SAE/AESI/Grade 3 or higher AE regardless of the seriousness, severity, or causality of the AE for which the subject discontinued will only occur for these secondary endpoints. The remaining summaries for safety will be presented as collected.

Population-level summary: Percent of subjects reporting any SAE or AESI assessed as related to trial vaccine within 8 days after vaccination, and percent of subjects reporting any Grade 3 or higher AE assessed as related to trial vaccine within 8 days after vaccination.

1.2 Trial Design

- Open label
- Phase 2
- Safety, tolerability, and immunogenicity trial
- Non-randomized
- 210 healthy, adult volunteers grouped as follows:
 - Group 1: Approx. 30 subjects determined to be seronegative for SARS-CoV-2 antibodies at screening (100 µg dose).
 - Group 2: Approx. 90 subjects determined to be seropositive for SARS-CoV2 antibodies at screening (100 µg dose).
 - Group 3: Approx. 90 subjects determined to be seropositive for SARS-CoV2 antibodies at screening (50 µg dose).

For this trial, in a run-in phase 6 adults (comprising of 3 subjects in each Group 1 and 2) will be vaccinated at 1 clinical trial site in a consecutive manner, with an at least 48 hours interval between the first and second subject of each group, then the third subjects dosed on consecutive days, before opening up to full enrollment of the trial. Safety assessments will be based on

solicited and unsolicited AE data through the first week after first vaccination for all 6 subjects, evaluated by an independent Data Monitoring Committee (DMC). After a positive DMC recommendation, enrollment to the rest of Groups 1 and 2 of the trial will commence. Group 3 subjects will be enrolled after completion of Group 2 enrollment. The total duration of subject participation in the trial will be up to 104 weeks (Groups 2 and 3, one-dose vaccination schedule) or 17 weeks (Group 1, two-dose vaccination schedule). The duration of the trial as a whole ultimately depends on the length of the recruitment period.

A temporary halting or termination for the trial as a whole can be decided in case of:

- an SAE and serious AESI with an at least reasonable possibility of a causal relationship to the administration of ABNCoV2 vaccine
- an unexpected Grade 3 or higher systemic reaction or lab toxicity with at least a reasonable possibility of a causal relationship to the administration of ABNCoV2 vaccine

These parameters are not all-inclusive. Other AEs could occur that would trigger a DMC review. Any member of the DMC, the Principal Investigator (PI) and/or the BN Medical Monitor could request a DMC review based on any observation.

Additional immunogenicity sample collection will be performed at 3 months after the last vaccination for all groups, and 6 months, 1 year, and 2 years for Groups 2 and 3 subjects. SARS-CoV-2 infection testing will be performed through the Active Trial Period if clinically indicated.

The schedule of events for Group 1 is in [Appendix 2](#) and for Groups 2 and 3 is in [Appendix 3](#).

2 Statistical Hypotheses

2.1 Multiplicity Adjustment

As no formal hypothesis testing will be performed, no adjustments for multiplicity will be needed.

3 Analysis Sets

The target analysis population for the trial includes subjects who meet all of the inclusion and none of the exclusion criteria as defined separately for each group (see Protocol Section 1.3). Subjects in Group 1 will be confirmed to be seronegative, and subjects in Groups 2 and 3 will be confirmed to be seropositive, and be stratified for enrollment by reason for seropositivity such that at least 40 subjects over both groups are enrolled for each of the three reasons for seropositivity (prior COVID-19 infection, prior mRNA vaccination, prior Adenovirus-based vaccination).

For the purposes of analysis, the following analysis sets are defined in [Table 1](#).

Table 1 Analysis Set Definitions

Participant Analysis Set	Description
Safety Analysis Set	All subjects who received at least 1 dose of ABNCoV2 vaccine. Subjects who are vaccinated are included in this set regardless of protocol violations or SARS-CoV-2 infection during the trial.
Immunogenicity Analysis Set	All subjects who are in the Safety Analysis Set and have at least 1 post-vaccination neutralizing antibody titer result. Subjects with protocol violations substantially affecting the immunogenicity outcomes will be excluded from this analysis set. For the purpose of the primary estimand, this includes SARS-CoV-2 infection prior to 2 weeks post last vaccination.

Protocol violations which may exclude a subject from the Immunogenicity Analysis Set may include, but are not limited to:

1. For Group 1, discontinuation prior to receiving both vaccinations
2. Enrollment into the incorrect SARS-CoV-2 exposure group, i.e., a seropositive subject enrolled into Group 1 or a seronegative subject enrolled into Group 2 or 3.
3. Major violation of the visit window affecting the immunogenicity results (i.e., the 2 weeks post-last vaccination serum sample is out of window).
4. Prohibited medication or vaccination given too close to the date of vaccination, or prior to collection of immunogenicity sample for the primary estimand time point, that may affect the immunogenicity results.
5. Major immunogenicity sample handling deviations at critical visits, e.g. regarding clotting time, turnaround time.
6. SARS-CoV-2 symptoms or infection prior to collection of the 2-week post-last vaccination immunogenicity sample.
7. Deviations with regard to vaccine preparation or administration.

Protocol violations leading to exclusion from the Immunogenicity Analysis Set will be reviewed on an ongoing basis, including reviews of the case report form data and protocol deviations as stored in the clinical trials management system. The final list of exclusions from the Immunogenicity Analysis Set will be approved at a data review meeting prior to the primary analysis reporting.

The following analysis sets will be used to obtain estimates of the primary and secondary estimands defined in the protocol, additional immunogenicity endpoints, and safety endpoints.

Table 2 Analysis Sets by Objective

Objectives	Analysis Sets
Analysis set for the primary estimand, supportive immunogenicity, and exploratory objectives	Immunogenicity Analysis Set Sensitivity for primary estimand: Safety Analysis Set with at least one post-baseline neutralizing titer, regardless of protocol deviations substantially affecting immunogenicity outcomes
Analysis set for secondary estimands and additional safety endpoints	Safety Analysis Set

4 Statistical Analyses

4.1 General Considerations

All individual data entered in the case report form will be listed as measured in subject-level data listings. Listings will be sorted by group, subject, time point, and parameter (if applicable), based on the domain presented. Tables for Group 1 will be created separately from Groups 2 and 3.

Subject population summaries including disposition, protocol deviations, demographics, medical history and baseline signs and symptoms, and prior and concomitant medications will be presented separately for seropositive and seronegative subjects:

Seropositive Table Columns

- Group 2
- Group 3
- Overall

Seronegative Table Column

- Group 1

For reporting of results collected at multiple visits (i.e., immunogenicity, vital signs, and laboratory measures) tables will be presented by time point and parameter.

In particular, Groups 2 and 3 tables for humoral immunogenicity endpoints will be presented with groupings based on each subject's baseline Wuhan strain neutralizing antibody titer value. The median of the values at or above the lower limit of quantitation (LLOQ) will be calculated from the pooled baseline values for Groups 2 and 3 data such that comparisons between dose levels and baseline neutralizing titer groups can be made. The following columns will be presented within each group:

- Overall
- Baseline NT <LLOQ

- Baseline NT \geq LLOQ
- Baseline NT \geq LLOQ - <Median
- Baseline NT \geq Median

Safety and secondary endpoint tables will be presented by group, without respect to baseline neutralizing antibody titer measure. Group 1 AE tables will be presented by vaccination period and for the Active Trial Period as a whole. Group 2 and 3 AE tables will be presented for the Active Trial Period (see [Section 4.1.3](#)). AEs will be summarized at both the event and subject level, with percentages based on subject counts.

With the exception of immunogenicity data, continuous measurements will be summarized using the number of observations (n), mean, standard deviation (SD), minimum (Min), median, and maximum (Max). Categorical data will be summarized using frequencies and percentages, unless otherwise stated.

Immunogenicity data which are log-normally distributed will be presented using n, geometric means and corresponding 95% confidence intervals (CI), median, Min, and Max. Figures will be scaled using a logarithmic y-axis.

Neutralizing antibody titers for the Wuhan strain will be scaled to WHO standard units (IU/mL), however neutralizing antibody titers for the variants of concern (e.g., alpha, beta, delta, and omicron strains) will be summarized as titer values. For all neutralizing antibody titer results, values below the lower limit of detection (LLOD) will be given a value of half value of the LLOD. Values that are below the LLOQ but at or above the LLOD will be analyzed as half the value of the LLOQ.

Total antibody titers by ELISA will also be scaled to WHO standard units (BAU/mL). Values below the LLOQ will be given a value of half of the LLOQ.

ELISPOT results will be presented as measured in spot forming units (SFUs)/ 10^6 PBMCs. Interferon- γ and Interleukin-4 results will be summarized separately within individual stimulant pools. Values below the LLOD will be given a value of half value of the LLOD. Values that are below the LLOQ but at or above the LLOD will be analyzed as half the value of the LLOQ. Values above the upper limit of quantitation (ULOQ) will be given a value of twice the ULOQ.

No statistical testing will be performed for the trial. All statistical summaries and analyses will be performed using SAS® version 9.4 or higher (SAS Institute, Cary, NC, USA).

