4.2 Primary Estimand Analysis

4.2.1 Definition of Endpoint

SARS-CoV-2 neutralizing antibody titers (Wuhan strain, presented in WHO standardized units of IU/mL) at 2 weeks after the last vaccination, i.e., after the second vaccination in initially seronegative subjects (Group 1) and after the single boost vaccination in initially seropositive subjects (Groups 2 and 3), for subjects in the Immunogenicity Analysis Set (Section [4.1.2](#)). For Group 1, this will be the neutralizing antibody titer collected at Week 6, and for Groups 2 and 3 it will be the neutralizing antibody titer collected at Week 2.

Serum samples will be collected from subjects as outlined in the trial procedure schedule [Appendix 2](#) and [Appendix 3](#). Immunogenicity testing will be performed at [REDACTED] and at contracted laboratories if needed. [REDACTED]

Neutralizing antibody titers to SARS-CoV-2 are assumed to be log-normally distributed. Values will be transformed to the \log_{10} scale for the purpose of analysis. Imputation of values based on limits of detection and quantitation are described in [Section 4.1](#). Once analyses are performed, estimates will be back transformed to the original scale for reporting.

The intercurrent event that may have an impact on the primary estimand is COVID-19 infection prior to the Week 6 or Week 2 neutralizing antibody titer collection, respectively, for all groups. As subjects who come in contact with the virus can have significant interference with the SARS-CoV-2 neutralizing antibody levels, these subjects will be excluded from the primary analysis. This is equivalent to the “while on treatment” strategy. Reasons for exclusion from the primary estimand analysis will be summarized separately for full accounting of the study population.

The second intercurrent event of discontinuing the study prior to collection of the neutralizing antibody titer endpoint at Week 6 or Week 2, respectively, for each group is not expected to have an impact on SARS-CoV-2 neutralizing antibody levels. Therefore, the “treatment policy” strategy will be used in these cases.

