4.2.2 Main Analytical Approach

The estimate of the primary estimand will be created using the Immunogenicity Analysis Set, which will include only subjects who have no protocol deviations that will substantially affect the immunogenicity outcomes. Due to this, missing values for the primary estimand analysis are unexpected. Subjects who have a value for the primary time point but developed COVID-19 symptoms prior to 2 weeks after the last vaccination, and had a positive PCR result for SARS-CoV-2 infection prior to the 2 weeks after the last vaccination time point, will be excluded from the analysis due to the interference the infection will have on the resulting neutralizing antibody results.

The geometric mean of SARS-CoV-2 neutralizing antibody titers (Group 1), and fold increases (Groups 2 and 3) 2 weeks after the last vaccination, will be summarized along with their 95% CIs. No statistical hypothesis testing will be performed for this single arm trial.

Geometric mean titers (GMTs) will be obtained by computing the arithmetic means and the corresponding 95% CIs on the \log_{10} scale, and then exponentiating the \log_{10} means and confidence limits to return the results to the original scale.

Fold increases for Groups 2 and 3 will be calculated as the ratio of the SARS-CoV-2 neutralizing antibody titer at 2 weeks post-last vaccination to the baseline neutralizing antibody titer (i.e., last measurement prior to vaccination). Geometric mean fold increases (GMFIs) will be calculated in the same manner as GMTs.

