In addition, as the missing pattern of titer values may not be monotone, i.e., subjects may be missing Week 2, Week 4, Week 5, or Week 6 neutralizing titer results, or a combination of these values, a fully conditional specification (FCS) method will be used. This method assumes the existence of a joint distribution for all variables used to predict the missing values and allows Week 2, Week 4, and Week 5 \log_{10} titer value to be imputed, if needed, to inform the missing Week 6 neutralizing titer values.

MI analyses will be performed in SAS using the PROC MI and PROC MIANALYZE procedures. A minimum of \log_{10} of half of the LLOQ will be set for imputed values to correspond to the observed data range. In addition, a seed of 19201 will be used for the procedure. The following is the sample code for the MI sensitivity analyses of the primary estimand for Group 1.

titersl: the dataset containing the \log_{10} neutralizing titer data along with the covariates used in the analysis, one record per subject.

sex: The sex identifier

yob: Year of birth

race: The race identifier

nvacc: Number of vaccinations received (1 vs. 2)

ltiterW2: \log_{10} Week 2 Titer Result

ltiterW4: \log_{10} Week 4 Titer Result

ltiterW5: \log_{10} Week 5 Titer Result

ltiterW6: \log_{10} Week 6 Titer Result

```

proc mi data=titersl out=titermi n impute=100 seed=19201 minimum=[log10LLOQ/2];
  class nvacc sex race;
  var nvacc yob sex race ltiterW2 ltiterW4 ltiterW5;
  fcs nbiter=20 reg(ltiterW6 = ltiterW2 ltiterW4 ltiterW5 nvacc yob sex race
    /details);
run;

proc means data=titermi n oprint nway;
  by _imputation_;
  var ltiterW6;
  output out=summ(drop=_type_ _freq_) n=n mean=logmn stderr=logse;
run;

ods output parameterestimates=grouplest;
proc mianalyze data=summ;
  modeleffects logmn;
  stderr logse;
run;
data grouplest2;
  set grouplest;
  GMT=10**estimate;
  GMT_LCL=10**LCLmean;
  GMT_UCL=10**UCLMean;
  keep estimate lclmean uclmean gmt:;
  label estimate='Mean Log10 Titers'
    lclmean='Lower 95% CI of the Mean Log10 Titers'
    uclmean='Upper 95% CI of the Mean Log10 Titers'
    gmt='Geometric Mean Titer'
    GMT_LCL='Lower 95% CI of the Geometric Mean Titer'
    GMT_UCL='Upper 95% CI of the Geometric Mean Titer'
run;

```

Groups 2 and 3 Multiple Imputation Procedure

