4.2.4 Supplementary Analyses

The primary analysis will be supported by descriptive summaries including medians, geometric means and corresponding 95% CIs, Min, and Max for each serum collection time point. These summaries will be performed for both the Immunogenicity Analysis Set and the Safety Analysis Set. No windowing or imputation will be applied for this summary, as they will be presented by the visit at which the serum sample was acquired.

A responder analysis will be performed, with response analyzed by serum collection time point. Response defined separately for naïve subjects (Group 1) and experienced subjects (Groups 2 and 3) as follows:

- Group 1: having SARS-CoV-2 neutralizing antibody titers above the LLOQ, or
- Groups 2 and 3: having an at least 2-fold, 4-fold, and/or 6-fold increase from baseline SARS-CoV-2 neutralizing antibodies.

For Group 1, subjects are required to have a negative qualitative SARS-CoV-2 test at screening to enter the trial. Despite this, there is a chance they have positive neutralizing titer at baseline. In this case, response would be defined as an at least 2-fold increase from baseline in neutralizing titer.

Response rates will be summarized for the Immunogenicity Analysis Set by time point as well as overall for the Active Trial Period, and corresponding 95% CIs will be calculated using the Clopper-Pearson method. The response rate analysis will also be repeated for the Safety Analysis Set with subjects missing a value for a time point, and not having achieved a response at a previous timepoint, counted as non-responders. For the final CSR, an over response rate will be calculated inclusive of the FU visits in addition to the Active Trial Period rates.

The primary analyses will also be performed within sex (male vs. female) and age groups as supportive analyses: 18 to < 50 years, 50 to < 65 years, 65 to < 75 years, and \geq 75 years. These summaries will be performed for the Immunogenicity Analysis Set only.

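### In Groups 2 and 3, two unquantifiable samples give a fold of LLOQ/LLOD, which counts as a 2-, 4- or 6-fold response if that ratio reaches 2, 4 or 6; the multiple-imputation floor also does not match the substituted data.

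*SAP*

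**What the plan says.** SAP 4.1 has two substitution rules for all neutralizing titers, Wuhan and variant:

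- Below LLOD: "values below the lower limit of detection (LLOD) will be given a value of half value of the LLOD".
- From LLOD up to LLOQ: "Values that are below the LLOQ but at or above the LLOD will be analyzed as half the value of the LLOQ".

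These values enter the log10 analysis. SAP 4.2.1 states "Imputation of values based on limits of detection and quantitation are described in" Section 4.1. SAP 4.2.2 then defines the fold: "Fold increases for Groups 2 and 3 will be calculated as the ratio of the SARS-CoV-2 neutralizing antibody titer at 2 weeks post-last vaccination", divided by the baseline titer.

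SAP 4.2.4 defines response differently by group:

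- "Group 1: having SARS-CoV-2 neutralizing antibody titers above the LLOQ, or" a 2-fold rise if the Group 1 subject already had a positive titer at baseline.
- "Groups 2 and 3: having an at least 2-fold, 4-fold, and/or 6-fold increase from baseline SARS-CoV-2 neutralizing antibodies".

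The Groups 2 and 3 rule sets no lower limit on the post-vaccination titer. Protocol 9.11 and 9.17 add none for these groups.

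For multiple imputation, SAP 4.2.3.2 specifies a minimum of log10 of half the LLOQ, for Group 1 and again for Groups 2 and 3. It says this minimum "will be set for imputed values to correspond to the observed data range".

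**The concern.** A fold increase is meant to describe the subject. When both samples are unquantifiable, and the first was undetected while the second was detected, the calculated fold is the ratio of two assay limits. It is the same for every such subject. If the limits are far enough apart, the subject counts as a responder with no quantified titer at either visit.

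The SAP provides for such baselines in Groups 2 and 3. Section 4.1 has a table column for baseline titers below LLOQ, and Section 5.1.1.4 has separate categories below LLOD and between LLOD and LLOQ.

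Response rates are reported by time point and for the Active Trial Period overall (SAP 4.2.4), and are plotted by variant strain (SAP 4.4). One such pair could therefore carry into the overall rate. In the Safety Analysis Set version, it could also keep a later missing visit from being scored as non-response, because that scoring applies only without an earlier response.

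The imputation floor is a second, separate mismatch. Imputed values cannot go as low as the values assigned to undetected samples.

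**Working it through.** The plan gives no figure on this point: no LLOD, no LLOQ and no ratio. What follows is algebra over an assumed range.

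**Inputs.** Substituted values LLOD/2 and LLOQ/2 (SAP 4.1); fold = post/baseline (SAP 4.2.2); thresholds 2, 4 and 6 (SAP 4.2.4); 90 subjects per seropositive group (SAP 6).

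**Fold for the pair.** Baseline below LLOD, post-vaccination titer between LLOD and LLOQ:

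(LLOQ/2) / (LLOD/2) = LLOQ/LLOD.

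Rescaling Wuhan titers to IU/mL by a constant factor leaves this ratio unchanged.

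**Effect on response and GMFI.** Compared with a fold of 1 for the same subjects, m such subjects out of 90 multiply the group GMFI by (LLOQ/LLOD)^(m/90).

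| LLOQ/LLOD (assumed) | Counts as response at | GMFI factor, m = 1 | m = 5 | m = 10 |
|---|---|---|---|---|
| 1.5 | none | 1.005 | 1.023 | 1.046 |
| 2 | 2-fold | 1.008 | 1.039 | 1.080 |
| 3 | 2-fold | 1.012 | 1.063 | 1.130 |
| 4 | 2- and 4-fold | 1.016 | 1.080 | 1.167 |
| 6 | 2-, 4- and 6-fold | 1.020 | 1.105 | 1.220 |
| 10 | 2-, 4- and 6-fold | 1.026 | 1.136 | 1.292 |

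The GMFI effect needs only LLOQ > LLOD; the response effect needs a ratio of at least 2.

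**Response rate.** Each such subject adds 1/90 = 1.1 percentage points. As an illustration, 60/90 = 66.7% (Clopper-Pearson 95% CI 55.9 to 76.3) becomes 65/90 = 72.2% (61.8 to 81.1) with five such subjects. In the column for baselines below LLOQ the denominator is smaller, so each subject counts for more.

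**Yardstick for the GMFI.** The SAP's half-width for Groups 2 and 3 reproduces: 1.96 × 0.5 × √(2 × 0.7) / √90 = 0.122 on the log10 scale. Ten such subjects at a ratio of 4 move the mean by 0.602 × 10/90 = 0.067, about half of that half-width.

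**Group 1.** Response needs a titer above LLOQ, so an unquantifiable sample cannot qualify. If a positive baseline means at least LLOD, its assigned value is at least LLOQ/2. An unquantifiable later value is at most LLOQ/2, so the fold is at most 1.

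**Imputation floor.** The stated minimum is log10(LLOQ/2), while the lowest observed value is log10(LLOD/2). The gap is log10(LLOQ/LLOD): 0.301, 0.602 and 0.778 at ratios of 2, 4 and 6. It is above zero whenever the two limits differ.

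**The case against.** The strongest case against is that the consequence cannot be shown from the documents. Below a ratio of 2 there is no response problem, and the limits are not public. The pattern needs an undetectable baseline in a subject who tested seropositive at screening, and then a titer still below LLOQ after a booster. A reader might infer that late visits and poorly neutralized variants will contain many such pairs. That is plausible, but no figure in the documents supports it. This part of the objection stands.

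A reader might also infer that the rule inflates the primary GMFI. It need not. A detected but unquantifiable baseline followed by an undetected sample gives LLOD/LLOQ, below 1. With r such reverse pairs the factor becomes (LLOQ/LLOD)^((m − r)/90), so the net direction is unknown. Response is one-sided, so reverse pairs do not offset added responders. Nor is it right to call every such responder false: undetected to detected may be a real rise of unknown size.

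The SAP's split by baseline titer is a partial safeguard. For Wuhan titers, every affected subject falls in the below-LLOQ and Overall columns. It does not isolate the affected variant results, because grouping uses the Wuhan baseline.

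On the floor, the objection is that imputation is a sensitivity analysis with few missing values expected (SAP 4.2.3.2). That limits the effect but does not reconcile the stated reason with SAP 4.1.

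**Conclusion.** The point holds conditionally, and for response it holds in Groups 2 and 3 only. Under SAP 4.1, 4.2.2 and 4.2.4 together, an undetected baseline followed by an unquantifiable post-vaccination titer has a fold of LLOQ/LLOD, and nothing in the plan stops it counting as a response once that ratio reaches 2, 4 or 6. Each such subject is worth 1.1 points in a group of 90. The ratio and the number of subjects are unknown, so the documents do not support a statement that the plan will produce artificial responders, or that Group 1 is affected.

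The mismatch in the imputation floor needs only LLOD < LLOQ, which the separate category between the two limits in SAP 5.1.1.4 implies.

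Both matters are minor. Response is a supplementary analysis, imputation is a sensitivity analysis, and there is no hypothesis testing (SAP 2.1).

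**What to change.** 1. In SAP 4.2.4, require for a Groups 2 and 3 response that the post-vaccination titer be at or above LLOQ, in addition to the fold criterion, for Wuhan and variant titers alike. This parallels the requirement already set for Group 1.
2. In SAP 4.2.3.2, set the imputation minimum to log10(LLOD/2) in the text and in both code samples. The Groups 2 and 3 sample shows its bracket without the logarithm, so write it on the log10 scale there too.
3. Keep the stated substitution for the primary GMFI. If wanted, add a sensitivity GMFI with LLOQ/2 for every value below LLOQ, as SAP 4.1 already does for ELISA.

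Replacing the primary substitution with a single value is not recommended. It would give two unquantifiable samples a fold of 1, but it would also divide the fold by LLOQ/LLOD for every subject with an undetected baseline and a quantifiable later titer. If 10% of subjects fit that pattern, the GMFI is multiplied by 2^(−0.1) = 0.93, 4^(−0.1) = 0.87 or 6^(−0.1) = 0.84 at ratios of 2, 4 and 6.

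The cost is one added condition, one changed constant and the matching programming. The downside is that a real rise that stays below LLOQ is no longer counted as a response, so rates may be slightly lower. The fix does not remove the effect of such pairs on the GMFI; the optional sensitivity analysis would show its size.
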